8.5.1.1 Short-Form Brief Pain Inventory (SF-BPI)

The SF-BPI is a self-administered standardized fifteen items questionnaire that assesses how pain interferes with or influences a participant's life. The query period covers the past 24 hours and takes 5 minutes for the participant to complete. The first item is a screening question about the participant's pain on the day. The questionnaire is then composed of pain drawing diagrams, four items about pain intensity (worst pain, least pain, average pain, pain right now), two items on pain relief treatment or medication, and one item on pain interference, with seven sub-items (general activity, mood, walking ability, normal walk, relations with other people, sleep, and enjoyment of life). The SF-BPI includes two main scores: a pain severity score and a pain interference score. The pain severity score combines the information of the four items about pain intensity, which are rated from 0, no pain, to 10, pain as bad as you can imagine. To derive the pain severity score the average of the four items will be taken. The pain interference is calculated similarly using the seven items regarding pain interference, which are rated from 0, does not interfere, to 10, completely interferes. The pain interference score will be the average of these seven items. Both scores will be between 0 and 10. The remaining items of the questionnaire do not contribute to the scoring. Higher scores correspond to a poorer condition of the participant. The first item, pain drawing diagrams (painful and most painful areas) and the items on pain relief treatment or medication (list of the treatments and amount of relief) do not contribute to the scoring. It has been validated ([Tan et al 2005](#), [Keller et al 2004](#)) for use with non-malignant pain populations and has been used in statin trials ([Cleeland 2009](#)).

The SF-BPI will be recorded as outlined in the Assessment Schedule ([Table 8-1](#)).

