8.5.1.2 Pain Diary

The Pain Diary is based on item-3 of SF-BPI. Daily pain will be rated on a numeric scale from 0 (no pain) to 10 (pain as bad as you can imagine) by the participants describing their pain at its worst in the last 24 hours. All participants will complete the diary via a handheld an electronic device. Investigators should instruct the participants to fill in the diary on a daily basis and to adhere to a certain routine for completing the diary.

8.5.1.3 SF-36 Version 2

The Short-Form Health Survey (SF-36) is a generic health-related quality of life (HRQoL) instrument which comprises of 36 questions across 8 domains: 1) limitations in physical activities because of health problems; 2) limitations in social activities because of physical or

emotional problems; 3) limitations in usual role activities because of physical health problems; 4) bodily pain; 5) general mental health (psychological distress and well-being); 6) limitations in usual role activities because of emotional problems; 7) vitality (energy and fatigue); 8) general health perceptions (Ware and Sherbourne 1992). Two overall summary scores, the physical component summary (PCS) and the mental component summary (MCS) will be computed (Ware 1994). An increase in the scale values reflects an improvement in the quality of life (Ware and Sherbourne 1992). The SF-36 is considered to be a valid, reliable, concise generic measure of state of health and has demonstrated to detect clinical treatment benefits across medical conditions including chronic disorders such as dyslipidemia (Hytinen et al 2008). The SF-36 is regularly used as a generic questionnaire in clinical studies in the field of cardiology (Müller-Nordhorn et al 2004) and is the most frequently used generic questionnaire in clinical studies with peripheral arterial disease (PAD) participants (Poku et al 2016). In the cardiovascular participant population, especially those with Coronary Heart Disease (CHD), it is considered to be the most reliable and change-sensitive generic questionnaire (Dempster and Donnelly 2000). The SF-36 has been validated at the international level for the chronically ill, including cardiac participants (Ware and Gandek 1998, Alonso et al 2004). In addition, the Health-related quality of life (HRQoL) project resulted in international reference values for the SF-36 for heart participants (Huber et al 2016). SF-36 will be recorded as outlined in Table 8-1.

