12.5.2.2 Muscle-related AE / SMQ rhabdomyolysis / myopathy

The proportion of participants experiencing at least one muscle-related AE as defined in the SMQ rhabdomyolysis / myopathy from day 1 to day 360 will be analyzed in a logistic regression model. Treatment and determined LDL-C target at screening will be included as factors in the model. The LDL-C targets depend on the participants' CV risk category and will be attributed directly from the CV risk category eCRF entries. Therefore, the CV risk category will be included in the model as the stratification factor ("very high risk", "high risk"). The odds ratio and its 95% confidence interval (CI) and p-value will be estimated. The null hypothesis of equal odds will be rejected within the confirmatory testing framework if the 1-sided p-value from the logistic regression model for the factor "treatment" is <0.025 .

Additionally, the relative risk as well as absolute risk difference and their 95% confidence intervals will be estimated from a Cochran-Mantel-Haenszel test (CMH) stratified for the determined LDL-C target before randomization based on the Score statistic.

In case of missing values muscle-related AE / SMQ rhabdomyolysis / myopathy will not be imputed but analyzed according to last known status of the occurrence of an event. To investigate the sensitivity to missing values or potentially different observation times in the two study arms, a time to the first experience of at least one muscle-related AE as defined in the SMQ rhabdomyolysis / myopathy will be conducted.

12.5.2.3 Number of days participants experiencing self-reported pain from day 1 to day 360

The number of pain days experienced will be analyzed using a negative binomial model (P. McCullagh and J.A. 1989) with the number of observed pain days as the dependent variable and treatment group and stratification factor (cardiovascular risk category: very high risk, high risk) as fixed-effect factors and log (follow-up duration in years) as the off-set. The annualized incidence rates and their 95% confidence intervals estimated from the model will be provided by treatment group. The treatment comparison will be performed through the estimated incidence rates. The incidence rate ratio and its 95% confidence interval will be provided.

12.5.2.4 Mean change from baseline in SF-BPI pain severity score and pain interference score at day 360

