2.1.1.5 Baseline

Baseline value is defined as the last non-missing value prior to the start of the treatment period, which means prior to the first injection of the blinded investigational treatment. If the date of assessment is the same as date of first injection but time is not available for comparison, the assessment is assumed to be prior to the administration of blinded investigational treatment. Questionnaires assessments at Day 1 are considered as baseline irrespective of time collected. Participants pain diary is not collected prior to first injection of the blinded investigational treatment, therefore baseline is not defined for the same.

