2.6.2.3 Annualized number of days with pain

Participant reported secondary endpoints are the number of days participants experiencing self-reported pain (at its worst in the last 24 h on a numeric rating scale from 0 (no pain) to 10 (pain as bad as you can imagine)) from Day 1 to Day 360 as reported in the electronic diary. A day with pain is defined as a day with a numeric score > 0. The annualized count (number of days pain) for each participant is calculated as the total counts during the study divided by the total individual observation time of that participant in the double-blind treatment period (between first dose of double-blind treatment up to the minimum of last contact date and Day 360 visit date) where pain diary was completed, multiplied by 365.25.

The null hypothesis to be rejected for the relevant secondary endpoint is:

- H_{04} : The annualized mean number of days pain is experienced is equal between both treatment groups.

The number of pain days experienced will be analyzed using a negative binomial model with the number of observed pain days as the dependent variable and treatment group and CV risk category as fixed-effect factors and the logarithmic follow-up duration (days between first dose of double-blind treatment up to the minimum of last contact date and Day 360 visit date where diary was completed) in years as the off-set. The annualized occurrence rates (i.e. number of pain days per year) and their 95% confidence intervals estimated from the model will be provided by treatment group. The treatment comparison will be performed through the estimated occurrence rates. The occurrence rate ratio and its 95% confidence interval will be provided.

If the negative binomial model fails to converge a quasi-Poisson model will be used instead.

Proportion of patients without any day with pain will be displayed descriptively where pain diary was completed.

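### The pain-day model (H04) has no baseline pain covariate, although a matching Day 1 worst-pain rating is collected and baseline SF-BPI already adjusts H05 and H06

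*SAP*

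**What the plan says.** **Model for H04.** SAP 2.6.2.3 specifies a negative binomial regression. Its terms are "the number of observed pain days as the dependent variable and treatment group and CV risk category as fixed-effect factors"; the offset is the log of diary-completed follow-up in years. SAP 5.5.2.3 repeats these terms. Protocol 12.5.2.3 already had the same list: "treatment group and stratification factor (cardiovascular risk category: very high risk, high risk) as fixed-effect factors". A pain day is any diary day scored above 0. Quasi-Poisson is named only as a fallback for non-convergence.

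**Diary question.** Protocol 8.5.1.2: "The Pain Diary is based on item-3 of SF-BPI", with participants "describing their pain at its worst in the last 24 hours" on a 0–10 scale. Protocol 8.5.1.1 lists worst pain among the four SF-BPI intensity items, on the same scale and with the same 24-hour recall.

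**Timing and status.** Table 8-1 schedules SF-BPI at screening and on Day 1. Protocol 6.3.2 places the injection after the visit's other assessments. SAP 2.1.1.5 says of the diary: "Participants pain diary is not collected prior to first injection of the blinded investigational treatment, therefore baseline is not defined for the same". Just ahead of that statement, the same section says of questionnaires: "Questionnaires assessments at Day 1 are considered as baseline irrespective of time collected".

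**Neighbouring endpoints.** For H05 and H06, SAP 2.6.2.4 includes the baseline SF-BPI score and its interaction with visit.

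**The concern.** Three confirmatory pain hypotheses share one family. Two adjust for pain before treatment and one does not, and neither document gives a reason. In H04, differences between participants in pre-existing pain stay in the residual variation, and a chance imbalance in them goes unadjusted.

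The H04 p-value also affects the other two tests. Under SAP 2.6.2.5 with one-sided α = 0.025, suppose H05 and H06 each have p = 0.02. If H04 has p ≤ 0.025, all three are rejected. If H04 has p > 0.025, none is, because 0.02 exceeds α/2 = 0.0125 and α/3 = 0.0083. Precision lost on H04 can therefore cost claims on H05 and H06.

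**Working it through.** **No figure to reproduce.** Protocol 12.8 and SAP 3 cover only the primary endpoint and muscle-related AEs. Neither gives an effect size, dispersion or power for H04. Everything below is conditional on assumptions.

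**Is the covariate legitimate?** It has the same question content, 0–10 scale and 24-hour recall as the diary. It is planned before dosing and is classed as baseline by the SAP. Yes.

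**Linear benchmark.** If adjustment scales the variance by 1 − r², power becomes Φ((z₀.₉₇₅ + z₀.₈₀)/√(1 − r²) − z₀.₉₇₅). From 80%, r = 0.3 gives 84%, r = 0.5 gives Φ(2.802/0.866 − 1.960) = 90%, and r = 0.7 gives 98%. The planned model delivers less than this.

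**Planned negative binomial model, simulated.** From the documents: 880 per arm, 1:1, one-sided 0.025. Assumed: rate ratio 0.9; mean daily pain probability 0.2 or 0.4; between-person SD of the daily-pain logit 1.5 or 3; correlation of Day 1 propensity with the year's propensity 0.5 or 1.0; 10% early exit. There were 1,500 trials per row. r is the resulting correlation of Day 1 pain with the pain-day rate. Arrows run from without to with the covariate.

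| Pain prob. | SD | r | Reported SE | Rejection rate | True variance, with/without |
|---|---|---|---|---|---|
| 0.2 | 1.5 | 0.22 | 0.0485 → 0.0476 | 0.601 → 0.610 | 0.99 |
| 0.2 | 1.5 | 0.49 | 0.0485 → 0.0444 | 0.590 → 0.645 | 0.86 |
| 0.2 | 3 | 0.29 | 0.0808 → 0.0792 | 0.201 → 0.225 | 1.08 |
| 0.2 | 3 | 0.70 | 0.0807 → 0.0720 | 0.212 → 0.311 | 1.10 |
| 0.4 | 1.5 | 0.26 | 0.0367 → 0.0358 | 0.857 → 0.872 | 0.99 |
| 0.4 | 1.5 | 0.53 | 0.0367 → 0.0325 | 0.861 → 0.917 | 0.88 |
| 0.4 | 3 | 0.33 | 0.0601 → 0.0587 | 0.380 → 0.423 | 1.12 |
| 0.4 | 3 | 0.73 | 0.0601 → 0.0521 | 0.391 → 0.535 | 1.09 |

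The SE falls by between 1 − 0.0476/0.0485 = 2% and 1 − 0.0521/0.0601 = 13%. Power rises by 0.9 to 14.4 points. The rate ratio estimate stays at about 0.90. True variance falls or stays level at SD 1.5 and rises at SD 3.

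The last row shows why power can rise without a gain in true precision. The unadjusted model reports 0.0601 when the true SE is 0.0444 (ratio 1.35). The adjusted model reports 0.0521 against 0.0464 (ratio 1.12). Part of the power gain is therefore a conservative SE moving towards the truth.

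**Type I error.** In two null scenarios, one-sided rejection went from 0.009 to 0.015 and from 0.009 to 0.026. Monte Carlo error at 0.025 is √(0.025 × 0.975/1500) = 0.004.

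**Quasi-Poisson with sandwich SE.** With pain propensity drawn from Beta(0.35, 0.65) and linked to item 3 by a Gaussian copula, the SE falls from 0.046 to 0.043, 0.042, 0.039 and 0.036 at r = 0.34, 0.44, 0.54 and 0.64. The variance reductions, from unrounded SEs, are 12%, 20%, 30% and 42%. The two ends equal 1/0.88 = 1.14 and 1/0.58 = 1.72 times the participants.

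With the same type of generator, the negative binomial SE falls only from 0.0667 to 0.0654, 0.0641 and 0.0621 at r = 0.33, 0.46 and 0.61. The true variance ratios there are 0.97, 1.08 and 1.28 (300 trials each).

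**Further check (200 trials per scenario).** Negative binomial power went 0.28 → 0.37, 0.32 → 0.39, 0.41 → 0.50 and 0.52 → 0.54. Quasi-Poisson with robust SE went 0.61 → 0.91, 0.64 → 0.74, 0.63 → 0.83 and 0.70 → 0.76.

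**The case against.** The strongest reply is that nothing is invalid. Randomisation makes the unadjusted comparison fair, chance imbalance is reflected in the confidence interval, and H04 is reached only after H01, H02 and H03 are all rejected. Under the model actually planned, the gain is modest and may lie in the reported SE alone. A single 24-hour rating is a noisy proxy for a year of pain days. CV risk category may also carry some pain information, since the very-high-risk stratum includes angina and PAD (Protocol 5.1).

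All of this stands, and it limits the point to efficiency. It does not explain why H04 alone among the three pain hypotheses is unadjusted.

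A reader might also infer that the covariate was dropped because the SAP believed no baseline pain measure existed. The documents do not show that: SAP 2.1.1.5 speaks only of the diary, and the protocol's model already lacked the term. Nor can the two items be called identical, since the protocol says only that one is based on the other.

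**Conclusion.** The point holds as a missed efficiency. A pre-dose covariate that matches the outcome, is already collected and is classed as baseline by the SAP is left out of H04, while its instrument's baseline scores are used for H05 and H06.

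Under the planned negative binomial model, adding it lowers the reported SE by roughly 2–13% and raises power by about 1–14 points. These figures rest on the assumed correlation (0.22 to 0.73), rate ratio and pain distribution, none of which the documents supply.

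Three stronger readings are not supported. First, the 12–42% variance reductions cannot be attached to the planned analysis: they belong to quasi-Poisson with sandwich SE, and the true variance ratio in the tabulated negative binomial runs was 0.86 to 1.12. Second, the adjustment is not free: it makes the negative binomial test less conservative, although simulated type I error stayed at or near 0.025. Third, the existing H04 analysis is neither biased nor shown to inflate type I error.

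**What to change.** Before unblinding, add two terms from Day 1 SF-BPI item 3 to the H04 model in SAP 2.6.2.3 and 5.5.2.3: any pain (0 versus above 0) and the 0–10 score. If Day 1 is missing, use the screening value. This agrees with the SAP's general definition of baseline as the last non-missing value before the first injection. For participants who went through run-in, that value predates statin up-titration and is a weaker proxy.

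Preferably pair the terms with a robust-variance fit (quasi-Poisson with sandwich SE). Pain days cannot exceed diary days, so the negative binomial is only approximate, and the gain is clearest with the robust fit. Because Protocol 12.5.2.3 names the negative binomial model and its terms, record either change in SAP section 4.

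No new data are needed. The costs are the added SAP text, a rule for participants with neither rating (the imputation in SAP 5.5.3 is not applied to pain days, which SAP 2.6.4 handles through the offset), and some loss of conservatism if the negative binomial is kept. If the sponsor prefers to leave H04 unadjusted, the SAP should say why and pre-specify the adjusted model as a sensitivity analysis.

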2.1.1.6 Post-baseline measurements / change from baseline

Post-baseline measurements are defined as assessments performed at and after start of blinded investigational treatment injection.

If absolute change from baseline is of interest, the change will be calculated as the difference between post-baseline value and the baseline value, if both values are not-missing. Relative change from baseline is given as the change from baseline relative to the baseline value times 100 (= [change from baseline / baseline value]*100), if baseline value is not zero and both values are not missing.

2.1.1.7 Visits

Measurements will be collected without windowing as defined in the protocol. Analysis windows will be used for analysis of the data as outlined in [Table 2-1](#).

Based on the study day a scheduled or unscheduled visit is performed, the visit will be allocated to the analysis visit within the corresponding analysis visit window. E.g., if the Day 30 visit of a participant is delayed and occurs on day 33 it will be allocated to analysis visit Day 30. In the case of deviations from the visit schedule, or due to unscheduled visits, several assessments of a participant may fall in a particular analysis window (either scheduled or unscheduled).

If two measurements are allocated to the same analysis window and one is scheduled and the other unscheduled, the scheduled visit will be prioritized regardless of the difference to the target day (even if the unscheduled visit is closer to target day). If at least two scheduled or at least two unscheduled visits are allocated to the same analysis window, the measurement closest to the target day/time will be used. In the event that two measurements are taken equally apart (e.g., one day before target date and one day after) and both are either scheduled or unscheduled the last one will be used.

In case an analysis visit for a specific assessment is not planned (e.g., vital signs at Day 60), the time span (in days) between two visits is split equally and mapped to the former or consecutive analysis visit window, respectively.

The mapped visits will be used in the 'by visit' analysis as allocated. However, the listings will contain all information regardless if the collected data is based on a mapped or not-mapped, scheduled or unscheduled visit.

Table 2-1 Analysis visit windows based on study days

Analysis window (study days)									
Analysis Visit	SF-BPI, GSRS, Clinical chemistry (if also in Limited Chemistry)	Clinical Chemistry (and not in Limited Chemistry)	Fasting lipid profile (includes LDL-C for efficacy analyses)	Hematology, Urinalysis	Fasting Lp(a)	PCSK9	Vital signs	SF-36	WIQ, Mac New, TSQM
Pre-dose	<= 1 pre-dose	<= 1 pre-dose	<= 1 pre-dose	<= 1 pre-dose	<= 1 pre-dose	<= 1 pre-dose	<= 1	<= 1	<= 1
Day 30	30 [1 post-dose, 45]	30 [2, 60]	.	.
Day 60	60 [46, 75]	.	60 [1 post-dose, 75]
Day 90	90 [76, 120]	90 [1 post-dose, 120]	90 [76, 120]	.	90 [1 post-dose, 225]	.	90 [61, 120]	90 [2, 150]	90 [2, 225]
Day 150	150 [121, 180]	150 [121, 180]	150 [121, 240]	150 [1 post-dose, 255]	.	.	150 [121, 180]	.	.
Day 210	210 [181, 240]	210 [181, 240]	210 [181, 240]	210 [151, 285]	.
Day 270	270 [241, 300]	270 [241, 300]	270 [241, 300]	.	.
Day 330	330 [301, 345]	330 [301, 345]	330 [241, 345]	.	.	.	330 [301, 345]	.	.
EOS/EOT (Day 360)	360 [≥346]	360 [≥346]	360 [≥346]	360 [≥256]	360 [≥226]	360 [≥1 post dose]	360 [≥346]	360 [≥286]	360 [≥226].

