6.6.1.2 Provisional dose levels

During visits at Day 30, Day 60 and Day 90, open label study treatment, rosuvastatin, will be sequentially titrated every 30 days until the participant's individual LDL-C is at target or until the participant achieves the MTD of rosuvastatin, whichever occurs first. For MTD definition please refer to [Section 3.4](#).

Dose adjustments have to follow the local SmPC, and recommended titration steps for rosuvastatin are 5 mg/day, 10 mg/day, 20 mg/day, and up to a maximum dose level of 40 mg/day, if indicated. In case rosuvastatin is not optimally titrated by Day 90, there is an optional visit at Day 120 for further optimizing rosuvastatin dose.

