Guidance issued by local regulatory bodies on this aspect prevail and must be implemented and appropriately documented (e.g. the presence of an impartial witness, sign/dating separate ICFs by trial participant and person obtaining informed consent, etc.).

Data protection measures

Participants will be assigned a unique identifier. Any participant records or datasets that are transferred to Novartis will contain the identifier only; participant names or any information which would make the participant identifiable will not be transferred.

The participant must be informed that his/her personal study-related data will be used by Novartis in accordance with local data protection law. The level of disclosure must also be explained to the participant who will be required to give consent for their data to be used as described in the informed consent

The participant must be informed that his/her medical records may be examined by Clinical Quality Assurance auditors or other authorized personnel appointed by Novartis, by appropriate IRB/IEC members, and by inspectors from regulatory authorities.

Novartis has appropriate processes and policies in place to handle personal data breaches according to applicable privacy laws.

8 Visit schedule and assessments

The Assessment Schedule ([Table 8-1](#)) lists all of the assessments when they are performed. All data obtained from these assessments must be supported in the participant's source documentation.

Participants should be seen for all visits/assessments as outlined in the Assessment Schedule ([Table 8-1](#)) or as close to the designated day/time as possible. Missed or rescheduled visits should not lead to automatic discontinuation.

Participants who discontinue from study treatment will be followed-up until the end of the study as indicated in the Assessment Schedule.

Participants who discontinue from study or withdraw their consent/oppose the use of their data/biological samples should be scheduled for a final evaluation visit if they agree, as soon as possible, at which time all of the assessments listed for the final visit (EOS) will be performed. At this final visit, all dispensed investigational product should be reconciled, and the AEs and concomitant medications not previously reported must be recorded on the eCRF.

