5.5.3 Multiple imputation

If not stated otherwise, imputation for primary and secondary analyses will be done by the following rules: For missing data, target day of the visit is considered to assess if missing is related or not related to intercurrent event. Absolute values are imputed corresponding endpoint variables are derived on imputed data.

Select data to fit the imputation model considering strategy applied for intercurrent events:

1. For primary endpoint all observed data will be included except for data collected after intercurrent events where composite strategy is applied, e.g. data collected after PCSK-9 inhibitors will be set to missing. Note, after death no data are collected, thus no need to take any action for while alive strategy. In case of occurrence of multiple intercurrent events e.g. double-blind treatment discontinuation and later PCSK-9 use, all data RDO data up to PCSK-9 inhibitor use will be used, others will be set to missing.
2. For secondary endpoints data all observed data will be included except for data collected after intercurrent events where hypothetical strategy is applied, these will be set to missing after intercurrent event. In case of occurrence of multiple intercurrent events e.g. double-blind treatment discontinuation and later PCSK-9 use, all RDO data up to

PCSK-9 inhibitor use will be used, others will be set to missing for LDL-C analyses where hypothetical strategy is applied for PCSK-9 inhibitor use.

3. Impute missing data using MAR (missing at random):

Select all participants, impute missing values at baseline and scheduled post-baseline visits, under assumption of missing at random (MAR), using the PROC MI procedure in SAS based on the fully conditional specification (FCS statement) method for 100 times and obtain 100 imputed datasets. Missing baseline values will be imputed using a model with treatment and CV risk category. Missing Day 30 values will be imputed using a model based on values of baseline, treatment and CV risk category. The same procedure will be repeated for subsequent visits.

This results in 100 imputed datasets.

For participants in the inclisiran treatment groups who discontinued double-blind treatment prematurely, set imputed values after discontinuation of double-blind treatment to missing, if not after occurrence of other intercurrent event such as PCSK-9 inhibitor, as these will be imputed using jump to reference (J2R) in step 4.

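### Allocating visits by study day can replace the observed Day 90 or end-of-study value with a late earlier visit, and leaves observed LDL-C slots to imputation

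*SAP*

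**What the plan says.** SAP 2.1.1.7 states that "Measurements will be collected without windowing as defined in the protocol". For analysis, each visit is placed by its actual study day: "the visit will be allocated to the analysis visit within the corresponding analysis visit window". Three rules then settle conflicts within a window:

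- Scheduled against unscheduled: "the scheduled visit will be prioritized regardless of the difference to the target day".
- Two of the same kind: if two or more scheduled, or two or more unscheduled, "visits are allocated to the same analysis window, the measurement closest to the target day/time will be used".
- Equal distance: if "both are either scheduled or unscheduled the last one will be used".

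No rule refers to the nominal visit. Unselected values appear only in listings. Protocol Section 8 asks for visits "as close to the designated day/time as possible" and gives no plus-or-minus limit.

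The primary endpoint is target attainment at Day 90 (SAP 2.5.1). H05 and H06 are tested at Day 360 (SAP 2.6.2.4), and H02 averages all post-baseline LDL-C visits (SAP 2.6.2.1). Where a slot has no value, SAP 5.5.3 has the programmer "impute missing values at baseline and scheduled post-baseline visits".

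**The concern.** The Day 60 and Day 90 visits, and the Day 330 and end-of-study visits, are only 30 days apart. Their windows meet at days 75/76 and 345/346. A participant who runs late can therefore have both visits of a pair in the later window. The closest-to-target rule then tends to pick the earlier one, because lateness moves it towards the next target while moving the later visit away.

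The two samples are not interchangeable. Protocol 6.6.1.2 says: "During visits at Day 30, Day 60 and Day 90, open label study treatment, rosuvastatin, will be sequentially titrated every 30 days". A sample drawn at the Day 60 visit cannot reflect a dose step decided at that visit; one drawn at the Day 90 visit can. Protocol 3.4 assumes that rosuvastatin is optimally titrated for most participants by Day 90. For affected participants, the primary endpoint would be read before one titration decision that the Day 90 visit was meant to capture. H05 and H06 would use the Day 330 questionnaire. H02 would lose observed values and gain imputed ones.

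**Working it through.** **Inputs**

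- LDL-C windows (SAP Table 2-1, lipid profile): Day 60 up to day 75; Day 90, days 76–120; Day 150, days 121–240; Day 330, days 241–345; Day 360 from day 346 with no upper limit.
- SF-BPI windows: Day 30 up to day 45; Day 60, days 46–75; Day 90, days 76–120; Day 270, days 241–300; Day 330, days 301–345; Day 360 from day 346.
- Post-baseline central lipid visits (Protocol Table 8-1): Days 60, 90, 150, 330 and 360. SAP 2.1.1.10 uses central-laboratory values only, so a Day 30 point-of-care value cannot fill the Day 60 slot.

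The SAP's own example, a Day 30 visit on day 33, is returned correctly as Day 30.

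**1. General condition.** Let the Day 60 visit fall on day a and the Day 90 visit on day b, with 76 ≤ a < b ≤ 120. The Day 60 sample is used when |a − 90| < |b − 90|. For a ≤ 90 this means b > 180 − a. By the same argument, a Day 330 visit on day a′ (346 ≤ a′ ≤ 360) displaces an end-of-study visit on day b′ when b′ > 720 − a′.

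| Day 60 visit on | Day 90 visit lost if on or after | Day 330 visit on | EOS visit lost if on or after |
|---|---|---|---|
| 76 | 105 | 346 | 375 |
| 80 | 101 | 350 | 371 |
| 85 | 96 | 355 | 366 |
| 88 | 93 | 358 | 363 |

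A late Day 60 visit alone is not enough. With Day 60 on day 80 and Day 90 on day 90, the Day 90 sample is kept.

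**2. Both visits s days late.** Put a = 60 + s and b = 90 + s. Then 90 + s > 180 − (60 + s) gives s > 15, and b ≤ 120 gives s ≤ 30. The Day 90 sample is lost for every s from 16 to 30. For the later pair, 360 + s > 720 − (330 + s) again gives s > 15, with no upper bound because the window is open.

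**3. Spacing kept.** If the visits stay at least 30 days apart and both fall in days 76–120, there are 15 + 14 + … + 1 = 120 possible day pairs, and all 120 lose the Day 90 sample. With at least 28 days it is 152 of 153; the exception is the tie at days 76 and 104.

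**4. Longer delays.** At s ≥ 31 the Day 90 visit falls on day 121 or later and moves to the Day 150 window. The Day 60 visit is then on day 91 or later and, until day 120 (s = 60), still supplies the Day 90 value without competition.

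**5. Emptied slots.** These come from the window edges, not from the closest-to-target rule.

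- LDL-C: Day 60 and Day 330 are both empty for a common s ≥ 16, unless an unscheduled central sample falls in the window. For s from 16 to 30, two of the five observed values (Day 90 and EOS) are dropped and two of the five slots are imputed.
- With Day 60 on day 80 and Day 90 on time, the Day 60 slot is still empty and its sample unused.
- SF-BPI: Day 330 is empty for s from 16 to 30. The Day 60 slot is filled by the equally late Day 30 questionnaire (30 + 16 = 46).

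**6. How many.** The documents give no distribution of delays. Assuming normal delays at both visits, simulation of the rule gives this displacement at Day 90, with counts per 1760:

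| Mean delay, SD (days) | Correlation 0 | Correlation 0.7 |
|---|---|---|
| 0, 3 | 0% (0) | 0% (0) |
| 0, 7 | 0.06% (1) | 0.65% (about 11) |
| 5, 7 | 1.2% (21) | 4.3% (75) |
| 7, 10 | 7.6% (133) | 13.9% (245) |

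With mean 0 and SD 5 it is under 0.1%.

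**The case against.** The best defence is that the endpoint is defined at Day 90, so a day-80 sample is more faithful than a day-110 sample, which includes titration time beyond Day 90. The rule is prespecified and blind to treatment. It also bites only when the earlier visit is at least 16 days late, which may be rare; the SAP's only example is a three-day delay.

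The rarity argument stands: the number may be close to zero. The proximity argument does not rescue the rule. Both visits took place, yet one observed value is discarded and, for LDL-C, a slot is imputed. The SAP itself already ranks scheduled above unscheduled visits whatever their distance from target, so calendar proximity is not its overriding principle.

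A reader might infer three stronger points that the documents do not support.

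- **A bias towards inclisiran on H01.** The protocol expects less intense background therapy with inclisiran, so losing a titration step could lower placebo attainment more. But Protocol 3.4 titrates in either arm when LDL-C is above target, the assumed attainment rates are redacted, and no Day 60 to Day 90 change is given for either arm. An effect on the odds ratio cannot be estimated. The second injection does not help the argument: Protocol 6.3.2 places injections after all other assessments at the visit, so neither sample reflects it.
- **That a 16-day slip is not a protocol deviation.** The full list of deviations is not in the documents, and SAP 2.1.1.7 itself speaks of deviations from the visit schedule.
- **That the Day 90 value is imputed.** It is replaced by an observed earlier value; imputation concerns the emptied earlier slot.

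**Conclusion.** The mechanism follows from the SAP text, and nothing elsewhere in the two documents prevents it. With a common delay of 16 to 30 days, the Day 60 sample is used as Day 90. With 16 days or more, the Day 330 value is used as Day 360. With unequal delays, the conditions in step 1 apply. The empty LDL-C slots are a separate consequence of the window edges and need their own remedy.

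The size is unknown. The range of about 0% to 14% rests entirely on assumed delay distributions, and its upper end needs a mean delay of 7 days, an SD of 10 and strongly correlated delays. No effect on H01, H02, H05 or H06 has been quantified, and the direction of any bias is plausible but not shown. This should be corrected because it affects the primary endpoint value and is cheap to correct, not because the primary conclusion is shown to depend on it.

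**What to change.** First count, from blinded visit dates, the participants whose Day 90 or Day 360 value would come from an earlier nominal visit. Then state in SAP 2.1.1.7, before database lock:

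1. Within an analysis window, the scheduled visit whose nominal day is that window's target takes priority over any other scheduled visit, whether or not the earlier window is empty.
2. A scheduled value not used for that reason is kept under its own nominal visit if that slot is otherwise empty.
3. A scheduled Day 90 or end-of-study value (central-laboratory or SF-BPI) is used for Day 90 or Day 360 even when a late earlier visit falls in that window, including when the Day 90 visit takes place after day 120.
4. Closest-to-target applies only to repeat samples of the same nominal visit, to several unscheduled samples, or when the nominal visit was not done.

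Priority must not depend on the earlier window being empty. For SF-BPI a late Day 30 or Day 270 questionnaire can fill that window, and from 31 days of common delay the LDL-C Day 60 and Day 90 samples no longer share one.

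The cost is a short paragraph and a small programming change. A few values will sit further from their target day, and an intermediate SF-BPI questionnaire may still go unused where a late neighbour occupies its slot.
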